Study protocol

Does investigator gender has an impact on patients perceived pain intensity after surgery?

Aim

The objective of this study is to investigate whether the gender of the investigator has an impact on patients reported levels of pain intensity after acute or scheduled surgery.

Background

Postoperative pain is a common problem after surgical procedures with many patients afflicted worldwide. Fundamental challenges are the complexity of measuring pain appropriately, and the many associated possible confounders. Over the last decades, gender of the investigator has been identified as a conceivable bias in the assessment and management of pain in experimental, as well as, clinical research. However, to our knowledge this issue has not so far been systematically investigated in a postoperative setting.

In a preclinical setting Levine et al. showed that male subjects reported less pain when evaluated by a female than by a male investigator, and this was followed by other similar studies indicating that the gender of the investigator may have an impact on the pain report Kallai et al. 2004, Gijsbers et al. 2005, Aslaksen et al. 2007 and Vigil et al. 2014. In a recent review Chapman et al. 2018 emphasize that it may have significant impact on experiments and clinical trials.

Methods

In this prospective paired cross-over study, two investigators of opposite gender independently obtain individually reported pain intensity levels in each study patient based on three different methods of pain assessment the Visual Analogue Scale (VAS), the Numeric Rating Scale (NRS), and the Painmatcher® (PM) technique based on electrical stimulation, at Malmö University hospital in Sweden.

Inclusion criteria is ongoing PACU care after recent surgery, age ≥ 18 years, cognitive and linguistic abilities to understand instructions and participate in the study, and perceived postoperative pain. All study participants receive oral and written study information and sign an informed consent form.

We have estimated to include around 50 patients per week, corresponding to around 600 patients in total, which we value to be enough margin verifying or rejecting the primary hypothesis of our study.

In each study session – from arrival at the PACU until approximately 15-minutes after arrival – the patients shortly describe, in words of their own, the main character of their postoperative pain. Afterwards they rate their current pain intensity level with the three different study techniques (VAS, PM and NRS in mentioned order). The investigators inform the patients equally verbally on how to carry out the pain measurements and the patients were blinded to the study aim of evaluating potential impact of investigator gender. Additional information on surgical and anaesthetic procedures, including current analgesic medication, is obtained from the peri-operative database of the hospital, and from individual patient records.

Study value

To further improve the postoperative care and pain relieve after acute and scheduled surgery it is of great importance to study biological, psychological and social factors affecting patients pain perception. More knowledge and awareness of investigator gender would possibly encourage caretaking and treatment of patients with pain and further on improved pain relief.

Statistical analysis plan

Study data is recorded in a Microsoft Excel spreadsheet. Non-parametric statistical tests will be used to evaluate study data reflecting pain intensity due to Visual Analogue Scale (VAS), the Numeric Rating Scale (NRS) and the Painmatcher®. With the Painmatcher® we obtained three values at each evaluation and the mean of these will be used for comparison. Pain intensity levels will be evaluated with respect to influence of investigator gender with the Wilcoxon signed-ranked test for dependent samples. Pain intensity levels will be compared between female and male study participants with the Mann-Whitney *U*-test. Reported pain descriptors will be analysed with qualitative methods. As is common in statistical practice we will adopt a significance level of $P < 0.05$.

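### The plan does not say how it is decided, balanced or recorded which investigator assesses first, so investigator gender can be confounded with order

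*Combined protocol and SAP*

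**What the plan says.** The Aim names one effect, that of investigator gender on reported pain. The design sentence in Methods is "In this prospective paired cross-over study, two investigators of opposite gender independently obtain individually reported pain intensity levels in each study patient". The only order that Methods fixes is that of the instruments: "rate their current pain intensity level with the three different study techniques (VAS, PM and NRS in mentioned order". The session is described as running "from arrival at the PACU until approximately 15-minutes after arrival", without saying whether that period covers one investigator's assessment or both.

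Two safeguards are given. Patients do not know that investigator gender is being studied, and "The investigators inform the patients equally verbally on how to carry out the pain measurements".

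The Statistical analysis plan section gives the test: "Pain intensity levels will be evaluated with respect to influence of investigator gender with the Wilcoxon signed-ranked test for dependent samples". On data capture it says "Study data is recorded in a Microsoft Excel spreadsheet" and lists no variables. For the Painmatcher it says "we obtained three values at each evaluation and the mean of these will be used for comparison", partly in the past tense, so some patients may already have been assessed.

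Neither the Methods nor the Statistical analysis plan says who assesses first, how that is decided, or whether it is written down.

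**The concern.** Each patient is rated twice, so every female-minus-male difference is also a first-minus-second or a second-minus-first difference. What separates the two is how order is assigned. Uniform instructions and patients' unawareness of the aim are useful, but they do not affect who goes first.

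A change between the first and second rating is plausible soon after arrival in recovery, through drift in pain or recall of the first answer. That is an inference; the documents do not report one. If there is such a change and the two orders are unequally used, the planned test attributes part of it to gender. A positive result could then be an order effect, and a null result could be a real effect offset by order. Investigator gender is the only effect in the Aim, so this bears on the study's main conclusion.

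**Working it through.** **Inputs.** From the plan: about 600 patients, the Wilcoxon signed-rank test and a significance level of 0.05 (two-sided assumed, since sidedness is not stated). Assumed, because the documents give none: SD of the paired VAS difference 15 mm, the order split, and the first-to-second shift. The plan gives no power calculation, so there is no figure of its own to reproduce.

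**Bias.** Let g be the true female-minus-male effect, d the mean second-minus-first shift and f the share of patients seen first by the female investigator. A female-first patient contributes g − d on average and a male-first patient g + d. The mean contrast is f(g − d) + (1 − f)(g + d) = g + d(1 − 2f), so the bias is d(1 − 2f). It vanishes if d = 0 or f = 0.5.

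If the shift differs by sequence, the bias is (1 − f)d_MF − f·d_FM, where MF and FM denote male-first and female-first patients. A 50/50 split that was not random can therefore still mislead: shifts differing by 2 mm leave a bias of 0.5 × 2 = 1.0 mm.

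**Scale.** The standard error is about 15/√600 = 0.61 mm, so a bias of 1 mm is already more than one and a half standard errors.

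**Type I error of the planned test, no gender effect** (simulated, n = 600, SD 15 mm, common shift):

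| Split | Shift d | Bias d(1 − 2f) | Error |
|---|---|---|---|
| 55/45 | 1 mm | −0.1 mm | about 5% |
| 55/45 | 3 mm | −0.3 mm | about 7% |
| 60/40 | 1 mm | −0.2 mm | about 6% |
| 60/40 | 3 mm | −0.6 mm | about 15% |
| 60/40 | 5 mm | −1.0 mm | about 33% |
| 70/30 | 3 mm | −1.2 mm | about 47% |
| 70/30 | 5 mm | −2.0 mm | about 88% |

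The result depends on the SD. At 60/40 with 5 mm, the error is 61% if the SD is 10 mm and 21% if it is 20 mm.

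Hand check of the 60/40, 5 mm row. The shift adds 4f(1 − f)d² = 4 × 0.6 × 0.4 × 25 = 24 to the variance, so the SD is √(225 + 24) = 15.8 and the standard error 0.644. Then 1.0/0.644 = 1.55, and the normal approximation gives a rejection rate of 34%.

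**Power for a true effect of +1.5 mm.** With no shift it is 67%. With d = 5 mm and f = 0.6 the expected contrast is 1.5 − 1.0 = 0.5 mm and power is about 10%. With f = 0.4 it is 1.5 + 1.0 = 2.5 mm and power is about 97%. The same shift can hide an effect or exaggerate it.

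**How likely is imbalance by chance?** If order were a fair coin toss for each of 600 patients, a split of 55/45 or worse has probability 1.6%, and 60/40 or worse about 1 in a million. The larger figures above therefore need a systematic cause, such as duty rosters.

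**After the fix.** With an exact 300/300 random split and a common shift, bias is zero and the signed-rank test is conservative, because the shift widens the observed differences without adding to the sampling error of their mean. The effective critical value is roughly 1.96 × √((225 + d²)/225), which is 2.00, 2.07 and 2.36 for d = 3, 5 and 10 mm. The corresponding errors are 4.6%, 3.9% and 1.8%; simulation gives about 4.5%, 4% and 2%. A Mann-Whitney comparison of first-minus-second differences between the two sequences holds about 5%. Its power for 1.5 mm is 67% with no shift, equal to the signed-rank test, and 67% against 63% with a 5 mm shift.

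**The case against.** The strongest reply is that the design label means something. A cross-over normally has both orders, and the session window of about 15 minutes, if it covers both investigators, limits how far pain can drift between ratings. Both points stand, and they make the extreme case (one gender always first) unlikely. Neither establishes equal or random order. A short interval does not rule out a shift either, and may favour recall of the first rating.

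A reader might infer that order is not recorded and that nobody could check it later. The documents do not support that. The spreadsheet sentence lists no variables at all, not even the pain scores, so its silence about an order field is uninformative. The accurate statement is that recording is not stated.

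A reader might also infer that the gender result is biased. That does not follow: bias needs both a shift and unequal order (or shifts that differ by sequence), and the documents show none of these. Small shifts do little harm, as the 1 mm rows show, and the 70/30 rows have no support in the documents beyond illustration.

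Finally, the signed-rank test might be blamed. It is not the defect. Under 1:1 random order it keeps its type I error at or below the nominal level.

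**Conclusion.** The concern holds as a design omission. The plan leaves the assignment, balance and recording of investigator order unstated and has no order element in its analysis, so a study that follows it to the letter can confound its only stated effect with order. Confidence is high for the omission. It does not extend to the presence or size of any bias, because split, shift and SD are all assumed. Within those assumptions the consequence runs from negligible (about 6% error at 60/40 with a 1 mm shift) to serious (about 33% with 5 mm). It should be fixed before further patients are assessed. If order was in fact randomised and recorded, one sentence in Methods and the observed split would settle the matter.

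**What to change.** **Design.** Assign investigator order (female-first or male-first) 1:1 from a blocked random list, and record the order and the clock time of each assessment. State this in Methods, and say whether the session window covers both assessments.

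**Analysis.** The planned signed-rank test may stay; it is valid and slightly conservative under blocked random order. As an efficiency gain only, the gender test could instead be the Mann-Whitney comparison of within-patient first-minus-second differences between the two sequences. That test assumes the same mean shift in both sequences. Random order supports this, but does not remove unequal carry-over.

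**Patients already assessed in a non-random order.** Report the order split where it is known and give the by-sequence analysis as a sensitivity analysis. It does not restore validity, because the sequences may differ in their shifts: at 60/40, shifts differing by 2 mm give that test an error of 34–35%. If only one order occurred, state that gender and order cannot be separated. If data collection is complete, this disclosure is all that remains possible.

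**Cost.** A random list, two spreadsheet columns, a few sentences in the SAP and occasional waiting by an investigator. No power is lost.

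### The planned signed-rank test compares the particular investigators used and cannot by itself support a claim about investigator gender in general

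*Combined protocol and SAP*

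**What the plan says.** The Aim is to "investigate whether the gender of the investigator has an impact on patients reported levels of pain intensity". The Study value section carries this into care: "More knowledge and awareness of investigator gender would possibly encourage caretaking and treatment of patients with pain". Both concern gender as a characteristic, not a contrast between named individuals.

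The Methods describe a paired design in which "two investigators of opposite gender independently obtain individually reported pain intensity levels in each study patient", with recruitment of "around 50 patients per week, corresponding to around 600 patients in total".

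The Statistical analysis plan names one type of test for the question, applied to the VAS, the NRS and the mean Painmatcher value: "Pain intensity levels will be evaluated with respect to influence of investigator gender with the Wilcoxon signed-ranked test for dependent samples". Its other quantitative test addresses the patient's own gender: "Pain intensity levels will be compared between female and male study participants with the Mann-Whitney" U-test.

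On making the investigators alike, the Methods say: "The investigators inform the patients equally verbally on how to carry out the pain measurements and the patients were blinded to the study aim". The documents do not state the total number of investigators, how they are assigned to patients, or whether the assessor's identity is recorded. They describe no analysis at investigator level.

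**The concern.** Pairing within the patient removes differences between patients. It does not remove differences between investigators. A woman and a man who assess the same patient may also differ in age, manner, appearance or profession, and a patient may respond to any of these. The signed-rank test attributes the whole paired difference to gender.

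The description of the two assessors can be read in two ways, and the problem arises under both:

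- **One woman and one man throughout.** Gender and person coincide. No analysis can separate them.
- **A pool from which one of each gender is drawn.** The test treats about 600 paired differences as independent, although many share an investigator. Variation between investigators is left out of the P value.

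The trial's main conclusion is at stake: a significant result could be reported as an effect of gender when it reflects the individuals used. Recruiting more patients does not help, because it shrinks the sampling error and leaves personal differences in place.

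**Working it through.** **The plan's own figure.** 600 patients / 50 per week = 12 weeks. The documents give no effect size, SD or power, so 600 cannot be reproduced as a power calculation.

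**Inputs.**

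- From the documents: n = 600 and a significance level of 0.05 (taken as two-sided, since sidedness is not stated).
- Assumed: SD of the within-patient difference, 15 mm on the VAS; between-investigator SD s, 0.25 to 2 mm; k investigators per gender, 1 to 5; investigators regarded as draws from a population.

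**Step 1: sampling error used by a patient-level test.** SD²/n = 225/600 = 0.375, so SE = √0.375 = 0.612 mm. An observed mean difference of 1.96 × 0.612 = 1.20 mm is enough for P < 0.05.

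**Step 2: false-positive rate for gender when there is no gender effect.** The mean paired difference has variance 2s²/k + SD²/n, but the test allows only for SD²/n. By normal approximation:

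rate = 2 × [1 − Φ(1.96 × 0.612 / √(2s²/k + 0.375))]

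Two examples with one investigator per gender:

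- s = 0.5: 2 × 0.25 + 0.375 = 0.875, square root 0.935; 1.96 × 0.612 / 0.935 = 1.283; rate 0.199.
- s = 1: 2 + 0.375 = 2.375, square root 1.541; 1.96 × 0.612 / 1.541 = 0.779; rate 0.436.

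| s (mm) | k = 1 | k = 2 | k = 3 | k = 5 |
|---|---|---|---|---|
| 0 | 5% | 5% | 5% | 5% |
| 0.25 | 9% | 7% | 6% | 6% |
| 0.5 | 20% | 13% | 10% | 8% |
| 1 | 44% | 31% | 24% | 17% |
| 2 | 68% | 57% | 49% | 39% |

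With the paired SD varied from 10 to 20 mm, s from 0.25 to 2 mm and k from 1 to 5, the rate runs from 5% to 78%.

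**Step 3: check on the signed-rank test itself.** Simulation (1,000 runs, SD 15 mm, s = 0 / 0.5 / 1 mm) gave 0.050 / 0.190 / 0.439 with one per gender and 0.043 / 0.085 / 0.163 with five. The formula gives 0.050 / 0.199 / 0.436 and 0.050 / 0.082 / 0.173. With no investigator variation the test holds its level, so the excess comes only from differences between individuals.

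**Step 4: one fixed woman and one fixed man.** Here no population of investigators need be assumed. If the two differ by d for personal reasons, the chance of P < 0.05 is Φ(d/0.612 − 1.96) + Φ(−d/0.612 − 1.96). This is 37% for d = 1 mm and 90% for d = 2 mm.

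**Step 5: can a small pool support a model that counts investigator variation?** In simulation (20,000 runs, balanced pairings, s = 0.25 / 0.5 / 1 / 2 mm) the investigator variance was estimated as zero in 60% / 53% / 35% / 15% of runs with two per gender and in 58% / 48% / 29% / 7% with three. A model fitted to so few investigators often cannot detect the variation it is meant to allow for.

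**The case against.** The best defence has four parts.

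**The safeguards.** Instructions are equal, patients do not know the aim, and the scores are the patients' own. This stands in part. These features reduce differences between investigators, but they do not equalise who the patient sees.

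**The number may be stated.** The Methods can be read as exactly two people for the whole study. On that reading the number is known and no other analysis would help. This stands: the matter is then a limit of design and interpretation, and only the conclusion needs to change. The k = 1 column above also depends on regarding the two as draws from a population that the documents do not define; Step 4 avoids that assumption.

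**The size is assumed.** This also stands. Every SD and every k is an assumption, and a range of 5% to 78% shows what is possible, not what will happen. The formula is a normal approximation; the Painmatcher was not simulated.

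**Remedies can be worse than the problem.** A permutation test on raw investigator means breaks the within-patient pairing, so differences between patients no longer cancel. With four per gender, s = 0.25 mm and an assumed true difference of 3 mm, simulated power is about 89% with no between-patient variation. It is about 51%, 30% and 15% at an assumed between-patient SD of 15, 20 and 25 mm. That remedy should not be used.

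A reader might infer that the signed-rank test is invalid, or that a significant result would be false. The documents support neither. The test is valid for the investigators used, and if they differ in nothing but gender it is valid for gender too.

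**Conclusion.** The concern holds as a gap between the aim and the analysis. Followed as written, the plan can report a difference between individuals as a gender effect, and it describes nothing that would let a reader tell the two apart.

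The size is unknown. Under the stated assumptions (paired SD 15 mm, investigators as draws from a population, s of 0.5 to 1 mm), the false-positive rate for gender is about 20% to 44% with one investigator per gender and about 8% to 17% with five. It returns to 5% when investigators do not differ. These figures should not be read as the trial's actual error rate, nor should the documents be taken to establish that only one woman and one man took part.

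The plan should be changed. The point bears on the main claim and costs little to address, but it does not make the paired comparison worthless.

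**What to change.** State in the Methods how many investigators of each gender take part. Record an investigator code for every assessment, if this is not already done. Then match the Statistical analysis plan to the number:

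1. **One woman and one man assess everyone.** Keep the signed-rank test and limit the conclusion to a difference between those two investigators.
2. **Several of each gender take part.** Keep the signed-rank test as a comparison of the investigators used. Base any general gender claim on an analysis that keeps the within-patient contrast and counts investigator variation, such as a mixed model with random patient and investigator effects and a small-sample correction. With only two or three per gender the investigator variance is too poorly estimated (Step 5), so limit the conclusion to the investigators used.

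Do not substitute a permutation test on raw investigator means.

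**Cost.** One data column and some SAP wording, with no change to patient procedures. The downside is a narrower claim or, with a pool, wider intervals and lower power, by an amount that depends on the unknown investigator SD and the number of investigators. The mixed model also brings a normality assumption on bounded scales.

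### About 600 patients is called enough to settle an unwritten primary hypothesis either way, but the plan has only P values and cannot show that investigator gender has no impact

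*Combined protocol and SAP*

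**What the plan says.** The Aim is an open, non-directional question: to "investigate whether the gender of the investigator has an impact on patients reported levels of pain intensity". The Methods refer to a primary hypothesis, but neither the protocol nor the SAP states one, and none of the three scales is named as primary.

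On sample size the Methods say "We have estimated to include around 50 patients per week, corresponding to around 600 patients in total", followed by the judgement "which we value to be enough margin verifying or rejecting the primary hypothesis of our study". No power, effect size, SD or margin is given.

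The Statistical analysis plan section has one method for the investigator question: "Pain intensity levels will be evaluated with respect to influence of investigator gender with the Wilcoxon signed-ranked test for dependent samples". On the threshold it says "As is common in statistical practice we will adopt a significance level of" P < 0.05, without saying whether tests are one- or two-sided. The Mann-Whitney test in the same section compares female with male participants, and the pain descriptors are analysed qualitatively, so neither addresses investigator gender. Nowhere is an estimate of the paired difference, a confidence interval or a smallest important difference mentioned.

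**The concern.** The sample-size sentence promises that the study can settle its hypothesis in either direction. If the hypothesis is that gender has an impact, rejecting it means concluding no impact. If the hypothesis is that it has none, verifying it means the same. On either reading one promised conclusion is absence of impact, and a significance test alone cannot supply it.

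Size matters here because of the use the sponsor foresees. The Study value section says "More knowledge and awareness of investigator gender would possibly encourage caretaking and treatment of patients with pain and further on improved pain relief". Whether that follows depends on how large any difference is. A bare P value cannot separate a trivial significant shift from a material one, and a non-significant P value does not show which differences remain possible.

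**Working it through.** **Inputs from the documents.** About 600 patients at "around 50 patients per week" (Methods); each patient rated by both investigators (Methods); Wilcoxon signed-rank test, P < 0.05 (Statistical analysis plan).

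**Assumptions.** Two-sided test, 600 complete pairs, and paired differences roughly normal unless stated otherwise. SDs of the paired difference are illustrative, because the documents give none.

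**1. The plan's own figure.** 600 cannot be reproduced as a power-based number, because nothing needed for that is stated. The only arithmetic available is 600 / 50 = 12 weeks of accrual, and no recruitment period is given.

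**2. What the test can detect.** The signed-rank test has efficiency 3/π relative to the paired t-test for normal differences.
- Effective n = 600 × 3/π = 573.0, with square root 23.94.
- Shift detectable with 80% power = (1.960 + 0.842) / 23.94 = 0.117 SD.
- Power at shift d (in SD) = Φ(23.94d − 1.960) + Φ(−23.94d − 1.960).

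| Shift (SD) | Power | Chance of P ≥ 0.05 |
|---|---|---|
| 0.117 | 80% | 20% |
| 0.10 | 67% | 33% |
| 0.05 | 22% | 78% |

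For assumed VAS SDs of 10 to 30 mm, 0.05 SD is 0.5 to 1.5 mm and 0.117 SD is 1.2 to 3.5 mm. In the other direction, a shift of 0.2 SD needs only ((1.960 + 0.842) / 0.2)² / (3/π) ≈ 206 pairs for 80% power.

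**3. Sensitivity to the distribution.** In 4,000 simulated trials of 600 pairs at a shift of 0.117 SD, with zero differences removed, the test rejected in 80% (normal), 97% (t with 3 df), 78 to 81% (rounded to whole points, SD 1 to 2) and 70% (whole points, SD 0.5). With no shift it rejected in 4.7 to 5.3%.

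**4. What an interval would add.** The 95% CI half-width for the mean paired difference is 1.964 × SD / √600 = 0.080 SD.
- VAS, assumed SD 10, 15, 20 or 30 mm: 0.8, 1.2, 1.6 or 2.4 mm.
- NRS, assumed SD 1, 1.5 or 2 points: 0.08, 0.12 or 0.16 points.

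**5. Which interval.** The usual companion to the signed-rank test, the Hodges-Lehmann CI, behaves poorly on whole-point scores. In 500 simulated trials at a shift of 0.117 SD with zeros kept, the share of trials with P < 0.05 in which each interval included 0 was:

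| Whole-point SD | Hodges-Lehmann CI | Mean-difference CI |
|---|---|---|
| 1 | 100% | 1.5% |
| 1.5 | 99.7% | 1.8% |
| 2 | 96% | 2.3% |

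In the 4,000-trial simulation, coverage of the mean-difference CI was 94.5 to 95.6%. Among significant trials it included 0 in about 2% with normal differences and about 15% with t, 3 df.

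**The case against.** The sample-size sentence can be read as everyday language for testing a hypothesis. That a superiority test cannot prove absence of effect is true of every such test, and a plan that lists tests does not forbid summary estimates. Part of this stands: the wording may be loose rather than a deliberate claim, and the SAP is silent on estimates rather than opposed to them. But nothing commits the sponsor to an estimate or to how a null result will be read, and an estimate chosen after the data are seen is weaker than one fixed beforehand.

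A reader might infer that real differences are likely to be missed. The documents do not support that. The 78% figure is for 0.05 SD, which is 0.5 to 1.5 mm on the assumed VAS SDs, and no smallest important difference is given against which to call that material.

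Another objection is that a mean does not belong in a non-parametric plan. It does treat scale points as equally spaced and is sensitive to outliers. Against that, the Wilcoxon test stays, and the SAP already averages scores for one scale: "With the Painmatcher® we obtained three values at each evaluation and the mean of these will be used for comparison".

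The objection to overreading the interval stands in full. It reflects the sampling of patients only. The Methods speak of two investigators of opposite gender, and neither document section says how the order of assessments is assigned. A female-minus-male difference may therefore contain individual-investigator or order effects and cannot by itself be read as the size of a gender effect.

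**Conclusion.** The point holds as a mismatch between the claim in the Methods and the analysis in the SAP. The hypothesis is unwritten, one of the two promised conclusions is absence of impact, and the only tool is a P value on each of three scales. It should be corrected.

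Three stronger readings are tempting and unsupported.
- **That 600 is too few.** Under normal differences and complete pairs, 80% power is reached at 0.117 SD and the CI half-width is 0.080 SD, so the number is probably ample for estimation. The true SD is unknown, and power shifts with heavy tails or coarse scoring.
- **That a non-significant result will be reported as no effect.** The plan does not say so; it leaves the reading open.
- **That 600 was derived from accrual.** The Methods place the accrual estimate beside the total but do not state it as the rationale.

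**What to change.** 1. Write out the primary hypothesis, two-sided to match the Aim, and name the scale on which it is judged. The choice among VAS, NRS and Painmatcher is the sponsor's. For example: in the same patient, pain intensity on the named scale differs between the report to the female and the report to the male investigator.
2. Keep the Wilcoxon test. Beside each P value report the mean paired difference (female minus male investigator) with its 95% CI. Do not rely on the Hodges-Lehmann CI alone for whole-point NRS. State that the interval reflects patient sampling only and may include individual-investigator or order effects.
3. State that P ≥ 0.05 alone will not be reported as no gender effect. A claim of equivalence is optional and would need a margin fixed before analysis.
4. Replace "which we value to be enough margin verifying or rejecting the primary hypothesis of our study" with wording such as: no formal sample-size calculation is given; around 600 patients are expected at around 50 per week; for illustration, 600 complete pairs give about 80% power (two-sided 5%) for a shift of 0.117 SD of the paired difference if differences are roughly normal.

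**Cost.** Wording changes and one estimate with CI per scale from data already collected, with no extra patients. The sample-size claim becomes less sweeping. The mean carries the limits noted above, and its CI can occasionally disagree with the Wilcoxon P value, so both must be shown.

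### Every patient is rated by both investigators, but no order or interval is stated and the only investigator-gender test ignores order and period

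*Combined protocol and SAP*

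**What the plan says.** The protocol's Methods section sets out the design: "In this prospective paired cross-over study, two investigators of opposite gender independently obtain individually reported pain intensity levels in each study patient". In each session the patient describes the pain and then rates it on three scales ("VAS, PM and NRS in mentioned order"). For the Painmatcher, the mean of three values per evaluation is used. The session runs "from arrival at the PACU until approximately 15-minutes after arrival".

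The Statistical analysis plan gives one analysis of investigator gender: "Pain intensity levels will be evaluated with respect to influence of investigator gender with the Wilcoxon signed-ranked test for dependent samples". The Mann-Whitney test that it also names compares female with male patients, not patients grouped by who assessed them first.

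Four things are not stated anywhere:
- which investigator goes first, or whether that is randomised or alternated;
- whether the order is recorded;
- the interval between the two assessments;
- any analysis by order, by period, or of first ratings alone.

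**The concern.** A paired comparison of two assessors is fair only if neither is systematically first, or if the analysis allows for order. Pain soon after arrival in the PACU can change between two ratings as anaesthesia wears off or analgesia takes effect. If one gender is first more often, part of that change enters the female-minus-male difference. The signed-rank test cannot separate the two, and if the order is not recorded no later analysis can either.

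A second issue is carry-over. The patient answers the same scales twice and may remember or anchor on the first answer. The second rating is then not a fresh report to the other investigator, and the paired difference shrinks. Only the first rating is free of this, and the plan does not analyse it separately.

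At stake is the answer to the study's single stated aim: the first issue can create a spurious effect or hide a real one, and the second can misstate its size.

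**Working it through.** **The plan's own figure.** About 600 patients at about 50 per week is 600/50 = 12 weeks of accrual. No effect size, SD, correlation or power is given, so 600 cannot be reproduced as a power calculation. It serves below as N.

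**Assumed inputs (none is in the documents).** VAS between-patient SD 23 mm; within-rating SD 8 mm; fall in pain between ratings f = 5 mm; share repeating the first answer c = 0.3; two-sided 0.05. Let p be the share of patients seen first by the woman.

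**1. Order and period, with no true gender effect**

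Women-first patients contribute +f on average to female minus male, and men-first patients −f, except those who repeat. So

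spurious mean = (2p − 1) × f × (1 − c).

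- p = 0.5: 0 mm
- p = 0.6: 0.2 × 5 × 0.7 = 0.70 mm
- p = 0.7: 0.4 × 5 × 0.7 = 1.40 mm

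The mean squared paired difference is 0.7 × (2 × 8² + 5²) = 0.7 × 153 = 107.1. At p = 0.6 the variance is 107.1 − 0.70² = 106.6, so SE = √(106.6/600) = 0.42 mm and z = 0.70/0.42 = 1.66. The chance of exceeding 1.96 is about 38%. At p = 0.7, SE = √((107.1 − 1.96)/600) = 0.42 and z = 3.34, giving about 92%.

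Simulation of the planned test under these assumptions agrees:

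| Women first | Signed-rank rejects true null | Order-adjusted test |
|---|---|---|
| 50% | 4% | about 5% |
| 60% | 36–40% | about 5–6% |
| 70% | 92–93% | about 5–6% |

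The size depends on the assumed fall. On a 0–10 scale with SD 2.5, correlation 0.7, a fall of 0.3 points and no repeaters, false rejection is 4% at balance and 11%, 31% and 81% when one gender goes first in 60%, 70% and 90%.

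**2. Carry-over, balanced order, true effect 5 mm**

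If a share c repeats the first answer, or all second ratings are pulled towards the first by a fraction c, the expected mean paired difference is (1 − c) × 5 mm:

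- c = 0.3: 3.5 mm
- c = 0.5: 2.5 mm
- c = 0.7: 1.5 mm

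In simulation the signed-rank test still rejected in 100% of trials at all three values. Power falls only for smaller effects. With 70% repeating it is 93% for 3 mm and 64% for 2 mm. For 0.3 points on the 0–10 scale (continuous ratings) it is 87%, 74% and 37% when 30%, 50% and 80% repeat.

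**3. First ratings only, 300 v 300**

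SD of one rating = √(23² + 8²) = 24.4 mm. With Mann-Whitney efficiency 0.955, SE = 24.4 × √(2/300)/√0.955 = 2.03 mm. For 5 mm, 5/2.03 − 1.96 = 0.50, so power is about 69%; simulation gives about 70%. The difference detectable with 80% power is 2.80 × SD × √(2/300)/√0.955 = 4.7, 5.9 or 7.0 mm for SD 20, 25 or 30 mm. The estimate stays at about 5 mm whatever the carry-over.

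**The case against.** The tempting stronger reading is that remembered ratings do carry over, that the paired test therefore understates any gender effect, and that a non-significant result could be put down to repetition. The documents do not support it.

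- Recall is inferred and no amount of it is documented. Carry-over of the opposite kind, where patients react against their first encounter, would inflate the contrast (0.30 to 0.38 points in one simulated case).
- The test's decision is robust. With 5 mm and 30–70% repeating it rejected every time, while the first-rating test managed about 70%. At 3 mm with 70% repeating the figures are 93% v 31%.
- The standard signed-rank test drops zero differences. Under exact repetition the remaining pairs still average about 5 mm, so the shrinkage in that case concerns the mean over all pairs, which the plan does not name as its estimate. Anchoring shrinks every pair.
- That the two ratings fall minutes apart is a reasonable reading of the session window, but no gap is stated, and it is unclear whether the window covers one investigator or both.
- The Painmatcher is a match to electrical stimulation ("With the Painmatcher® we obtained three values at each evaluation and the mean of these will be used for comparison"). Recall is more plausible for VAS and NRS.
- Patients are blinded to the aim, instructions are equal and the investigators work independently.

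All of this stands, and it limits the carry-over point. It does not touch the order point: blinding and equal instructions do not stop pain changing between ratings. Nor do the documents show that order was unbalanced; they are silent. The false-rejection figures are therefore conditional, and they belong to order and period rather than to carry-over.

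**Conclusion.** The point holds in two parts of unequal weight.

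The main part is that investigator order and interval are unspecified and the sole gender test ignores both. If order is unbalanced and pain changes, the test is biased. Under the assumed 23/8 mm SDs, 5 mm fall and 30% repeaters, false rejection is about 40% at 60% women-first and about 90% at 70%; a smaller fall gives less. At balanced order it is at or below 5%. The direction depends on who goes first and which way pain moves.

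The lesser part is possible attenuation. If patients recall or anchor, the mean paired difference shrinks by the carried share. At N=600 this mainly distorts the size of the effect; it costs power only for small effects with heavy repetition. The amount cannot be derived from the documents.

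This should be corrected, but a reader should not infer that the paired design is unusable or that first ratings should replace it.

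**What to change.** 1. Randomise 1:1 which investigator assesses first, record the order for every patient, and state the intended interval between assessments.
2. Make the investigator-gender test order-adjusted: compare first-minus-second differences between the two order groups with a Mann-Whitney test. A common period change cancels, and half the shift between the groups estimates the gender difference. This removes period bias but not attenuation.
3. Pre-specify, as a sensitivity analysis, a first-rating comparison of patients first seen by the woman with those first seen by the man: Mann-Whitney, with the Hodges-Lehmann shift and 95% CI.
4. Report the share of identical pairs for each scale.

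The cost is an allocation list, one protocol sentence, one changed test and one added analysis on data already being collected. The order must be set and recorded prospectively. The downside is that the first-rating comparison is between patients and much less precise (about 70% power for 5 mm under the assumed SDs). It should inform interpretation, and a conclusion of no effect should not be made to depend on it.
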